5.4.2.3 Radiographic Progression-Free Survival

rPFS is defined as the time from initiation of study intervention to the first objective evidence of radiographic progression or death due to any cause (whichever occurs first). Radiographic disease progression is defined as soft tissue (non-bone) disease progression per RECIST v1.1 or confirmed progression of bone disease per PCWG3 criteria. Participants who continue treatment beyond initial disease progression will be considered to have progression of disease (PD) at the time of the initial progression event.

Participants who do not have radiographic PD at the time of analysis will be censored as follows:

- Participants who do not have radiographic PD and are still on study at the time of analysis will be censored at the date of the last tumor assessment documenting absence of progressive disease
- Participants who have discontinued study treatment and have started subsequent anti-cancer therapy or had subsequent cancer surgery or radiation prior to documentation of radiographic PD will be censored at the date of the last evaluable tumor assessment prior to the initiation of subsequent treatment.
- Participants who discontinued the study prior to documentation of radiographic PD will be censored at the date of the last tumor assessment documenting absence of progressive disease.
- Participants who do not have radiographic PD and who die more than 16 weeks from their last evaluable tumor assessment will be censored at the date of the last tumor assessment documenting absence of progressive disease. Participants who within 16 weeks of their last evaluable tumor assessment will be considered as having an event at the date of death.

rPFS will be estimated using Kaplan-Meier techniques, and the median survival time and 95% CIs will be estimated within each cohort. If median survival is not reached, survival times and 95% CIs will be reported at deciles that are estimable given the observed events.

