Radiographic disease assessment	X	Per PCWG3 guidelines: Every 8 to 9 weeks (± 1 week) for first 24 weeks, and every 12 weeks (± 1 week) thereafter until radiographic PD or start of subsequent therapy. Refer to the cohort appendix for each respective combination for cohort-specific details							
Review of alternate anticancer therapy ^o								X	X
Follow-up for overall survival								X	X

ADA = anti-drug antibodies; AE(s) = adverse event(s); AESI(s) = adverse event(s) of special interest; cfDNA = cell-free deoxyribonucleic acid; ECG = electrocardiogram; ECOG = Eastern Cooperative Oncology Group; EOT = end of treatment; I/E = inclusion/exclusion; PCWG3 = Prostate Cancer Clinical Trials Working Group 3; PD = progressive disease; PD-1 = programmed cell death 1; PK = pharmacokinetics; Q3M = every 3 months; SAE(s) = serious adverse event(s)

^a Tests/procedures performed as standard of care prior to obtaining informed consent and within 28 days prior to the first day of study intervention administration do not have to be repeated at screening.

^b The End of Treatment Visit will be completed following the last dose of study intervention, either at completion of the on-treatment phase or at early discontinuation.

^c For up to 2.5 years from the initiation of study intervention, participants in the follow up phase will be contacted by the site to collect alternate anticancer therapy information and determine survival status.

^d Informed consent must be obtained prior to any study-specific procedures and may be obtained prior to the 28-day screening window.

^e Body weight may be required more frequently for study interventions using weight-based dosing. Combination-specific frequency will be provided in the cohort appendix for each respective combination.

^f Blood samples should be collected prior to administration of any study intervention.

^g 12-Lead ECG will be collected at screening, Cycle 2 and Cycle 4.

^h Circulating tumor cells will be collected at baseline (ie, Day 1 of Cycle 1 prior to study intervention administration), Day 1 of each cycle (prior to study intervention administration), and EOT.

ⁱ cfDNA (blood) will be collected at baseline (ie, screening visit prior to study intervention administration), Day 1 of Cycle 2 and Cycle 4, and EOT.

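### The fixed 16-week limit on counting deaths in rPFS does not match the 12-weekly scan schedule, and its censoring bullets overlap with no stated order

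*SAP*

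**What the plan says.** SAP 5.4.2.3 defines rPFS as time to "first objective evidence of radiographic progression or death due to any cause (whichever occurs first", with no limit on how long after the last scan a death may fall. Its list of censoring rules then sets one. Participants without radiographic progression "who die more than 16 weeks from their last evaluable tumor assessment will be censored" at the last scan showing no progression. The companion sentence says that those "within 16 weeks of their last evaluable tumor assessment will be considered as having an event at the date of death"; the verb 'die' has dropped out of it. Another bullet says that participants who have stopped study treatment and started other anti-cancer therapy, or "had subsequent cancer surgery or radiation prior to documentation of radiographic PD will be censored" at the last evaluable scan before that treatment.

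Protocol 1.3, Table 1, sets scans as "Every 8 to 9 weeks (± 1 week) for first 24 weeks, and every 12 weeks (± 1 week) thereafter", and adds: "Refer to the cohort appendix for each respective combination for cohort-specific details". The cohort appendices are not among the documents reviewed.

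Protocol 9.3.1.2 also counts death from any cause. The only rPFS censoring it states is at the start of subsequent anti-cancer therapy, and it has no death limit. SAP Section 6, which lists differences from the protocol, has no entry for rPFS. The SAP gives no reason for choosing 16 weeks.

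**The concern.** A limit on how long after the last scan a death still counts is usually meant to ask whether the participant had gone unobserved for too long. That question depends on how often scans are due. A single number of weeks gives different answers before and after week 24: the same behaviour (one missed scan, then death) is an event early and often a censoring later.

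The deaths concerned will usually be known, because Protocol 7.2 collects survival status every 3 months for up to 2.5 years. Those affected have missed a scan, or have stopped scanning because the investigator judged that clinical benefit was lost, which Protocol 8.1 allows and which can precede radiographic progression. Kaplan-Meier estimation treats censoring as unrelated to prognosis, and that is doubtful for this group.

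The overlap between bullets is a separate matter. Two programmers could follow the text faithfully and derive different rPFS data. In a cohort of 15 or 30, one participant is 1/15 = 6.7 or 1/30 = 3.3 percentage points at the start of the curve.

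**Working it through.** **The plan's own figures.** None is given for rPFS. The only design calculation is the two-stage design for the composite response rate (SAP 3.3). It reproduces: stopping after Stage 1 under 10% is 0.9^15 + 15 × 0.1 × 0.9^14 = 0.549 (stated 55%). The exact two-stage sum gives type I error 0.068 (stated 0.07) and power 0.774 (stated 77%). None of these depends on rPFS.

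**Limit against schedule.** Inputs: 16 weeks (SAP 5.4.2.3); intervals of 8, 9 and 12 weeks, each ±1 week (Protocol Table 1). The longest gap with no missed scan is interval + 1 + 1. After one missed scan, the second interval is the time from the missed scan to the next one due.

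| Schedule | 16 weeks in intervals | Longest gap, none missed | Two nominal intervals | Part of second interval where death is censored |
|---|---|---|---|---|
| 8-weekly | 16/8 = 2.00 | 10 weeks | 16 weeks | 0 of 8 weeks |
| 9-weekly | 16/9 = 1.78 | 11 weeks | 18 weeks | 2 of 9 weeks (22%) |
| Across the change (scan at week 16, week 24 missed, next due week 36) | not constant | 10 weeks | 8 + 12 = 20 weeks | 4 of 12 weeks (33%) |
| 12-weekly | 16/12 = 1.33 (16/13 = 1.23 to 16/11 = 1.45) | 14 weeks | 24 weeks | 8 of 12 weeks (67%) |

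Every gap with no missed scan is below 16 weeks, so the limit never touches a participant who attends as scheduled.

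**Overlap of the bullets.** Take a last scan at week 16 without progression, new therapy at week 20, and death at week 28. Under the subsequent-therapy bullet this is censored at week 16. Under the death bullet the death is 28 − 16 = 12 weeks after the last scan, so it is an event at week 28. Nothing says which applies.

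**How many participants might be affected.** The documents give no rates of missed scans or of stopping scans, so these are illustrations only.

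- *Illustration 1.* Independent exponential times; median progression 17, 26 or 39 weeks paired with median survival 52, 65 or 78 weeks; scans at weeks 8, 16 and 24, then every 12; 4,000 simulated participants per scenario; subsequent therapy not modelled. With 10% of scans missed and no other loss, 0.8 to 1.5% of participants are known deaths turned into censorings (0.015 × 30 = 0.45 of a participant at most). If 10 to 20% stop scanning at each scheduled scan for deterioration, with 5% of scans missed, the share is 14 to 29% (0.14 × 15 = 2.1 to 0.29 × 15 = 4.4 participants in a cohort of 15). A two-interval limit, modelled as 18 weeks before week 24 and 26 after, lowers it only to 13 to 27%. In this second setting, the median under the SAP rule equalled the all-deaths median with the fastest progression, and was 3 to 12 weeks shorter in the other scenarios.
- *Illustration 2.* Gamma frailty linking the risks; median radiographic progression 20 to 30 weeks; 19 to 37% leaving for deterioration; median later survival 20 to 40 weeks; four scenarios. The 52-week event-free percentages under the SAP rule, a 25-week limit, and scanning continued to progression were 29.9/29.1/26.5, 30.0/28.5/24.5, 30.0/27.9/22.8 and 41.3/40.0/35.7. The SAP rule is high by 3.4, 5.5, 7.2 and 5.6 points. The wider limit recovers 0.8, 1.5, 2.1 and 1.3 of these, or 24, 27, 29 and 23%. Counting every death at its own date moved the estimate the other way.

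**The case against.** Censoring a death that follows a long unscanned gap is a recognised choice. Protocol 9.3 leaves variable definitions and missing-data handling to the SAP and lets the SAP prevail. A reader might infer that the rule contradicts the rPFS definition and is simply an error. The documents do not support that: the SAP states an event definition and then explicit censoring rules for it. What stands is that the choice is unexplained, is not matched to the schedule and is not listed. Section 6 calls itself a high-level overview, so the missing entry is a matter of transparency only.

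A reader might also infer that a third of deaths after a 12-weekly scan are lost, from 8/24 weeks. That assumes everyone who survives 12 weeks then misses a scan, while those who attend lose nothing.

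The practical reach is limited. The primary analysis comes once all participants in a cohort have 6 months of follow-up or have discontinued (SAP 3.4). A death more than 16 weeks after a week-24 scan falls after week 40, so at that analysis only participants enrolled earlier could contribute one. Cohort expansion uses the composite response rate (SAP 5.7.1). Cohort appendices may set a different scan schedule, which would change the 1.33. All of this lowers the priority, but none of it resolves the mismatch under the core schedule or the overlap between bullets.

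**Conclusion.** The point holds in a limited form. Under the core schedule the 16-week limit equals two intervals only at 8-weekly scanning. After week 24 it is 1.33 intervals, and 8 of the 12 weeks following one missed scan fall outside it. The conflict between the subsequent-therapy and death bullets is plain from the text and needs no assumption.

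The effect on the estimates is not established. With occasional missed scans alone it is about 1% of participants. It becomes material only if a sizeable share stop scanning before radiographic progression, a rate the documents do not give. A reader might infer that late rPFS is overstated. The illustrations do not settle this: one puts the SAP estimate above fully observed rPFS, while the other puts the SAP median at or below the median with all deaths counted. A reader might also expect a wider window to remove the problem. It recovers about a quarter of the simulated gap, because most of the loss comes from scanning having stopped.

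No error rate, power or sample size changes. Priority is low to moderate: rPFS is a secondary endpoint with no hypothesis test, but the study's stated purpose is to give estimates for designing later studies.

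**What to change.** 1. Replace the 16 weeks with the date of the second scheduled scan after the last evaluable scan, plus the visit window. Take the dates from the schedule that applies across the week-24 change and from any cohort-appendix schedule. This gives about 16 + 1 = 17 to 18 + 1 = 19 weeks early on, about 20 + 1 = 21 weeks when the last scan was at week 16, and 24 + 1 = 25 weeks once scans are 12-weekly (26 if the last scan was itself a week early). A rule based only on the interval in force at the last scan would fail at the change.
2. Add a sensitivity Kaplan-Meier analysis that counts every death without prior progression and before subsequent anti-cancer therapy as an event at the date of death. This is consistent with Protocol 9.3.1.2, which censors at the start of such therapy. Show it beside the main analysis, without assuming that it is the conservative one.
3. State that the subsequent-therapy bullet is applied before the death bullet, again consistent with Protocol 9.3.1.2, and restore the missing verb 'die'.
4. List the rPFS censoring rules in SAP Section 6. Include the censoring date for subsequent therapy, which is the start of therapy in the protocol and the last prior scan in the SAP.

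The cost is SAP wording and one extra Kaplan-Meier run per cohort. No new data are needed.

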1.3 SCHEDULE OF ACTIVITIES

The Schedule of Activities (SOA) shown in [Table 1](#) provides a general overview of the types and timing of the tests and procedures that will be performed in this study. The combination-specific tests and procedures, as well as the timing, will be described in the cohort appendix for each respective combination and will supersede the general overview provided here.

Table 1: Schedule of Activities

Tests & Procedures	Screening/ Enrollment ^a	On-Treatment: Immunotherapy Combination Treatment					End of Treatment ^b	Follow up	
		Cycle 1	Cycle 2	Cycle 3	Cycle 4	Cycle 5 Onward			
Day		To be determined based on immunotherapy combination Refer to the cohort appendix for each respective combination for details on combination-specific timing							14 - 28 days after last dose
Window (days)	-28		± 3	± 3	± 3	± 3	± 7	± 10	± 14
Informed consent ^d	X								
Review of I/E criteria	X								
Medical and cancer history	X								
Physical examination	X	X	X	X	X	X	X		
ECOG performance status	X	X	X	X	X	X	X	X	
Vital signs (see Section 8.2.3)	X	X	X	X	X	X	X		
Body weight ^e	X			X		X (every 3 cycles)	X		
Hematology (see Table 4)	X	X ^f	X ^f	X ^f	X ^f	X ^f	X	X	
Clinical chemistry (see Table 4)	X	X ^f	X ^f	X ^f	X ^f	X ^f	X	X	
Urinalysis	X						X		
Prostate-specific antigen	X	X	X	X	X	X	X	X	
Testosterone level	X								
12-lead ECG ^g	X		X		X				
Circulating tumor cells ^h		X ^f	X ^f	X ^f	X ^f	X ^f	X		
cfDNA (blood) ⁱ	X		X ^f		X ^f		X		
Circulating soluble analytes/PK/ADA ^j	X	X ^f	X ^f	X ^f	X ^f		X		
Blood immune biomarkers ^j	X	X ^f	X ^f	X ^f	X ^f		X		
Archival tumor tissue	X								

Tests & Procedures	Screening/ Enrollment ^a	On-Treatment: Immunotherapy Combination Treatment					End of Treatment ^b	Follow up	
		Cycle 1	Cycle 2	Cycle 3	Cycle 4	Cycle 5 Onward			
Day		To be determined based on immunotherapy combination Refer to the cohort appendix for each respective combination for details on combination-specific timing						14 - 28 days after last dose	110 days after last dose
Window (days)	-28		± 3	± 3	± 3	± 3	± 7	± 10	± 14
Tumor biopsy ^k	X		X				X (at PD [optional]) ^k		
Stool collection ^l	X		X						
Concomitant medications	X	X	X	X	X	X	X	X	
Adverse events	All AEs/AESIs/SAEs will be collected for at least 100 days after the last dose of study intervention ^m								
Immunotherapy combination administration ⁿ		Refer to the cohort appendix for each respective combination for details on study intervention administration							

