8.1 EFFICACY ASSESSMENTS

Participants will undergo tumor assessments as designated in the SOA (see [Section 1.3](#)) regardless of dose delays, until loss of clinical benefit as determined by the Investigator (unless the participant withdraws consent, or the Sponsor terminates the study). All participants who discontinue study intervention for reasons other than disease progression (eg, AEs) will continue tumor assessments for up to 2.5 years from initiation of study intervention or until study completion, death, disease progression, loss to follow-up, withdrawal of consent, or study termination, whichever occurs first. At the Investigator's discretion, tumor assessments may be repeated at any time if PD is suspected.

Measurable and evaluable lesions should be assessed and documented at screening. Tumor assessments performed as standard of care prior to obtaining informed consent and within 28 days prior to the first dose of study intervention do not have to be repeated at screening.

Screening assessments must include computerized tomography (CT) scans (with IV contrast unless contraindicated and oral contrast as appropriate per institutional standards) of the chest, abdomen, and pelvis. A spiral CT scan of the chest may be obtained but is not a requirement. If a CT scan with contrast is contraindicated (ie, in participants with contrast allergy or impaired renal clearance), a non-contrast CT scan of the chest maybe performed and magnetic resonance imaging (MRI) scans of the abdomen and pelvis should be performed. If the participant has a known history of brain metastases or is symptomatic in the opinion of the Investigator, scans of the head should be obtained.

If a CT scan for a tumor assessment is performed in a positron emission tomography (PET)/CT scanner, the CT acquisition must be consistent with the standards for a full contrast diagnostic CT scan.

Bone scans (technetium-99m [TC-99m]) should be performed at screening if clinically indicated. If bone metastases are present at screening and cannot be seen on CT or MRI scans, or if clinically indicated, TC-99m bone scans should be repeated when complete response (CR) is identified in target disease or when progression in bone is suspected.

CT scans of the neck or extremities should also be performed if clinically indicated and repeated throughout the study if there is evidence of disease at screening.

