9.3.1.2 Secondary Efficacy Endpoints

The secondary efficacy endpoints include:

- ORR: A composite endpoint where response is defined as a participant meeting at least one of the following:
 - CTC response: Change from unfavorable (≥ 5 cells/7.5 mL of blood) to favorable (≤ 4 cells/7.5 mL of blood). Participants with a baseline CTC value < 5 cells/7.5 mL of blood will not be evaluated for this criterion.
 - Prostate-specific antigen (PSA) response: Confirmed PSA response is defined as $\geq 50\%$ reduction in PSA from baseline, with a repeat assessment confirming the result at least 3 weeks later. Participants without a PSA value at baseline and at least two post-baseline assessments will not be evaluable for this criterion.
 - Confirmed response of CR or partial response (PR) by objective radiographic disease assessment using modified RECIST version 1.1 (ie, CR or PR and no progression in bone per the PCWG3; [Scher et al., 2016](#)). Per RECIST, to be assigned a best overall response of CR or PR, changes in tumor measurements must be confirmed by repeat assessments that should be performed no less than 4 weeks after the criteria for response are first met. Participants who received at least 1 dose of the combination study intervention or component of the combination but do not have RECIST assessment for any reason will be counted as not responding.
- Disease control rate (DCR) at 9 months: Defined as CR, PR, or stable disease (SD) for 9 months as best response by PCWG3-modified RECIST 1.1. Participants who received at least 1 dose of the study intervention combination or component of the combination but do not have RECIST assessment for any reason will be counted as not responding.

- Radiographic progression-free survival (rPFS): Defined as time from initiation of study intervention to the first objective evidence of radiographic progression, or death due to any cause (whichever occurs first). Radiographic disease progression includes soft tissue disease progression per PCWG3-modified RECIST 1.1 and confirmed progression of bone disease per PCWG3 criteria. Participants who continue treatment beyond initial disease progression will be considered to have PD at the time of the initial progression event. Participants who do not have radiographic progression will be censored at initiation of subsequent anti-cancer therapy.
- OS: Defined as the time from initiation of study invention until death due to any cause.
- OS rate at 12 months.

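### The fixed 16-week limit in the rPFS death rule does not match the 12-week scan interval after week 24, and no rule covers participants with only a screening scan

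*SAP*

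**What the plan says.** The definition in SAP 5.4.2.3 puts no time limit on death: "rPFS is defined as the time from initiation of study intervention to the first objective evidence of radiographic progression or death due to any cause". The last censoring bullet of that section adds one. Participants without radiographic progression "who die more than 16 weeks from their last evaluable tumor assessment will be censored at the date of the last tumor assessment" that showed no progression. The companion sentence, which lacks its verb, covers earlier deaths: "Participants who within 16 weeks of their last evaluable tumor assessment will be considered as having an event at the date of death".

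The scan schedule is in Protocol 1.3, Table 1: "Every 8 to 9 weeks (± 1 week) for first 24 weeks, and every 12 weeks (± 1 week) thereafter". Section 1.3 adds that combination-specific timing "will be described in the cohort appendix for each respective combination and will supersede the general overview provided here". Under Protocol 8.1, standard-of-care tumor assessments made "within 28 days prior to the first dose of study intervention do not have to be repeated at screening", so the baseline scan can precede time zero by four weeks.

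Protocol 9.3.1.2 has no gap rule for deaths. The only censoring it names for rPFS is at a change of therapy: "Participants who do not have radiographic progression will be censored at initiation of subsequent anti-cancer therapy". SAP Section 6, which lists differences from the protocol, has no rPFS entry.

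**The concern.** A limit on the gap between last scan and death is meant to censor deaths that follow a long unobserved period, conventionally two missed assessments. A fixed number of weeks does that only if the scan interval is constant, and here it is not. The same record (one missed scan, then death before the next one) is treated differently according to when it happens.

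The limit also runs from the scan date, while rPFS runs from first dose. For a participant with no post-baseline scan the two clocks differ by up to four weeks, and the SAP does not say where such a participant is censored.

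At stake is whether a death counts as an event in cohorts of 15 to 30, where one participant of 15 is 6.7 percentage points. If scans are missed because a participant is failing, the censoring is informative.

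**Working it through.** **Plan's own figure.** None is given for rPFS. The only design calculation is the two-stage rule on CRR (continue at 2 or more of 15, success at 6 or more of 30). It reproduces: type I error 0.0684 (stated 0.07), power 0.7745 (77%), early termination 0.549 (55%). It does not involve rPFS.

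**Inputs.** Limit of 16 weeks (SAP 5.4.2.3); intervals of 8, 9 and 12 weeks, each scan ±1 week (Protocol Table 1); screening scan up to 4 weeks before first dose (Protocol 8.1).

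**No missed scan.** Longest gap = interval + 1 + 1 = 12 + 2 = 14 weeks. From a day -28 scan to a first scan at week 9 + 1 = 10, the gap is 4 + 10 = 14 weeks. Both are below 16, so the rule never fires.

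**One missed scan.** The gap to the next scheduled scan is 2 × interval, plus 2 weeks with windows. Exposed weeks are those beyond 16.

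| Interval | Gap, nominal | Gap, with windows | Exposed, nominal | Exposed, with windows |
|---|---|---|---|---|
| 8 weeks | 16 | 18 | 0 | 2 |
| 9 weeks | 18 | 20 | 2 | 4 |
| 12 weeks | 24 | 26 | 8 | 10 |

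Example: scan at week 36, week 48 missed, death at week 53. The gap is 53 − 36 = 17 weeks, so the death is censored at week 36.

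Given exactly one missed scan, and death uniform over the interval before the next, the censored shares are 0/8 = 0%, 2/9 = 22% and 8/12 = 67%.

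**Screening scan only.** With the scan at day -28, the limit expires at study week 16 − 4 = 12. If only the week 8-9 scan is missed, a death between week 12 and week 16-18 is censored at week -4.

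**Size.** The documents give no event or missed-scan rates, so these are assumptions: exponential times with medians of 26 or 52 weeks, scans at weeks 8, 16, 24 and then every 12, scans missed independently, screening scan uniform over the 4 weeks before dose, 130 weeks of follow-up, 20,000 simulated participants per setting. Expected number per 15 = 15 × (share dying without documented progression) × (share of those censored).

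| Median PD / death (weeks) | Missed scans | Die without documented PD | Of these, censored | Per 15 |
|---|---|---|---|---|
| 26 / 52 | 10% | 0.386 | 0.039 | 0.23 |
| 26 / 52 | 20% | 0.398 | 0.089 | 0.53 |
| 52 / 52 | 10% | 0.518 | 0.044 | 0.34 |
| 52 / 52 | 20% | 0.533 | 0.093 | 0.74 |
| 52 / 26 | 10% | 0.704 | 0.031 | 0.33 |
| 52 / 26 | 20% | 0.723 | 0.071 | 0.77 |

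Other runs reached 10% censored at 20% missed. In the settings tabulated, 60-81% of the censored deaths followed a single missed scan, and 15-26% were placed at the screening scan, at or before time zero.

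**Effect on the estimate.** In the same row order, medians under the 16-week rule against counting all deaths were 21.0 v 22.1, 24.0 v 24.0, 29.0 v 29.7, 30.8 v 29.1, 18.5 v 18.8 and 18.7 v 19.2 weeks. The differences go both ways. With no missed scans the rules coincide, yet separate runs still differed by up to 1.8 weeks (29.1 v 27.3), so these differences are within simulation noise. The late curve is overstated by about 0.001-0.005 with random missingness, and by up to about 0.01 when scans are missed because of progression.

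**The case against.** The strongest reply is that the harm is slight and its direction uncertain. A reader might infer that rPFS is overstated throughout, because failing participants lose their events. The documents do not establish that, and the calculations do not bear it out. Under the all-deaths definition a participant stays in the risk set until death, so the curve before that death can be higher. In one assumed setting the all-deaths median was longer (18.2 against 17.2 weeks). This part of the reply stands; only a small late overstatement remains.

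Four further points are fair:

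- The 67% share is conditional on one missed scan and death before the next. It is not a share of all deaths.
- SAP 3.4 times the primary analysis at a minimum of 6 months of follow-up. After a week-24 scan and a missed week-36 scan, censoring needs a death after week 24 + 16 = 40, which only participants with longer follow-up can reach.
- Cohort appendices, not available here, may set another scan schedule.
- SAP Section 6 calls itself a high-level overview, and Protocol 9.3 leaves variable definitions and missing data to the SAP. The omission there is therefore a minor point.

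Whether a screening scan can serve as the last assessment without progression is also open. The SAP does not exclude it. If it does not count, the participant has no censoring date, so a rule is missing on either reading.

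**Conclusion.** The point holds as a mismatch between the rule and the core schedule, and as a missing rule for participants with no post-baseline scan. After week 24 one missed or unevaluable scan can turn a death into a back-dated censoring. With a screening scan only, the limit can expire at week 12 and the literal date precedes time zero.

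The expected effect is under one participant per 15 at 10-20% randomly missed scans, with little or no shift in the median and about 0.01 or less on the late curve. These sizes rest on the assumed medians and missed-scan rates and on the default schedule.

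Two stronger readings should be resisted. Affected participants do not leave the analysis: they remain in the population and are censored early, though one censored at or before time zero contributes no time at risk. Nor is a one-missed-scan death in the first 24 weeks always an event, since the 9-week grid and an early screening scan both leave exposed weeks. OS, the safety analyses and the CRR-based expansion rule are unaffected.

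**What to change.** In SAP 5.4.2.3:

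- Replace the fixed 16 weeks with censoring only when death follows two or more consecutive missed scheduled assessments, windows included, on the schedule that applies to the cohort. On the core schedule this is 2 × 8 + 2 = 18 to 2 × 9 + 2 = 20 weeks early on, and 2 × 12 + 2 = 26 weeks in the 12-week phase.
- State that with no post-baseline scan the gap is counted from first dose and any censoring is placed at day 1.
- Restore the missing verb in the bullet's second sentence.
- Report the protocol definition, with all deaths as events, as a sensitivity curve, without presuming that it will be shorter.

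List the rule in SAP Section 6.

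The cost is SAP wording, one extra Kaplan-Meier curve per cohort, and a late rPFS curve that may look marginally lower.
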